#### **8.1.1. IMPLANT REMOVALS**

During this clinical investigation, the implant may be removed at any time at the request of the study subject and/or if the investigator believes it appropriate (eg, cataract surgery). An implant removal is considered a Secondary Surgical Intervention and requires the completion of a Serious Adverse Event Form (see Section 12). Test article will not be provided for IOL replacement. Subjects with implant removals will not be exited from the study.

### ***8.2. Methods Used to Minimize Bias***

Randomization and masking are not used in this study. However, all investigators and study coordinators will receive common training (including specular image collection and angle measurements) to ensure consistent application of the methods specified in the protocol. Also, the same inclusion criteria are to be applied by all investigators and all patients meeting inclusion criteria will be invited to participate in the study. Furthermore, explanted subjects will not be discontinued. Bias will also be minimized by using a central reading center for corneal endothelial cell analysis. In addition, study duration will be sufficient to examine the effect of the lens on endothelial cells (ie, density [REDACTED]).

### ***8.3. Clinical Study Termination***

An investigational site can be suspended or terminated by the Sponsor if monitoring or auditing identifies serious or repeated deviations. While possible, it is not anticipated that the entire study will be terminated. If the study or an investigational site is terminated, the investigator and any regulatory authorities will be informed with 5 days of the decision. Investigators would be given instructions for the procedures to be followed to assure that adequate consideration is given to the protection of the patient's interests. The investigator will be responsible for informing IEC/IRB's of the early termination of the trial or of the investigational site.

### ***8.4. Regulatory Documentation and Records Retention***

Essential documents must be retained by the Investigator for as long as needed to comply with national and international regulations (generally 2 years after discontinuing clinical development or after the latest marketing approval). The Sponsor will notify the Investigator(s)/institution(s) when the study-related records are no longer required.

### ***8.5. Data Management***

A Clinical Data Management System (CDMS) will be used to collect and validate clinical data. The CDMS will conform to the Sponsor's requirements for system setup and data security. Data validation will be performed by electronically generated checks and manual reviews. Final data and related documentation will be retained according to the Sponsor's retention schedule.

### ***8.6. Data Review and Handling***

Clinical data captured at the sites will be entered into electronic case report forms (eCRFs) within the CDMS. SAS datasets (SAS Institute Inc. Cary, NC , USA) for the clinical data will be downloaded from the electronic data capture (EDC) database after database lock, or as needed throughout the clinical trial. All SAS datasets will be housed in a secured network area storage and will be accessible to the Sponsor using read only roles. The datasets will reflect the current protocol. The datasets will reflect the current state of the database, all

previous actions and values of the data will be captured in the audit trail within the EDC database.

Any change or correction to data reported on a CRF will be updated and/or explained within the CDMS. The original entry and all actions applied to the CRF after initial entry will be maintained in the audit trail (ie, an audit trail will be maintained that documents the action, user and date of change or explanation).

[figure not shown]
#### **8.7. *Data Publication***

Results will be published through clinicaltrials.gov.

## 9. STUDY PROCEDURE

### 9.1. Study Visits and Examination

An Entrance Visit will be completed upon a subject's enrollment. Subjects may enroll in the study at any time, thus the Entrance Visit may coincide with any visit (Year 4/4A to Year 10/10A ).

Postoperative visits for the first and second implants may be performed simultaneously if both visits fall within the proper timeframes specified for each eye.

Subjects examined subsequent to Day 3740 and prior to study exit (eg, a planned visit occurring after the last study plan visit) will be included in the Year 10/10A analysis if:

a) no Year 10 or 10A Form was received previously, or
b) the original Year 10 or 10A exam was early, or
c) the subject was previously unavailable for the visit or previously discontinued.

Each required examination must be recorded on the corresponding electronic Case Report Forms (eCRFs) in a timely manner.

## **9.2. *Entrance Visit***

The following information will be recorded on the Entrance Visit eCRF:

### **9.2.1. INFORMED CONSENT**

Prior to undergoing study specific measurements, subjects will be asked to give informed consent and sign the Institutional Review Board (IRB) or Institutional Ethics Committee (IEC) approved Informed Consent Document (ICD). Only subjects who have signed the informed consent and qualified to be in the study by meeting all inclusion criteria will be enrolled into the study.

The Investigator, or designee, will explain the clinical trial to each potential subject and the subject must indicate voluntary consent by signing and dating the approved informed consent form. The subject must be provided an opportunity to ask questions of the Investigator, and if required by local regulation, other qualified personnel. The Investigator must provide the subject with a copy of the consent form written in a language the subject understands. The consent document must meet all applicable local laws and will provide subjects with information regarding the purpose,

procedures, requirements, and restrictions of the clinical trial, along with any known risks and potential benefits associated with the investigational product, the available compensation, and the established provisions for maintaining confidentiality of personal, protected health information. Subjects will be told about the voluntary nature of participation in the clinical trial and will be provided with contact information for the appropriate individuals should questions or concerns arise during the clinical trial. The subject also will be told that their records may be accessed by appropriate authorities and Sponsor-designated personnel. The Investigator must keep the original, signed copy of the consent and must provide a duplicate copy to each subject.

#### **9.2.2. INCLUSION CRITERIA**

[figure not shown]
Refer to the list of Inclusion criteria in Section 7.2. to ensure that the subject meets all qualifications for participation (ie, inclusion criteria).

#### **9.2.3. ENROLLMENT INFORMATION**

Record the following information from the subject's previous (C-02-23, C-02-40, C-03-21, or C-05-57) study: Protocol number, investigator number, subject number, study eye(s), whether or not the lens was replaced, and the Visit in which the subject entered the C-09-043 study. If the fellow eye has been implanted with any Phakic IOL (at any time), or if the ACRYSOF CACHET Lens has been replaced with another IOL, please record lens information ("other IOL").

[figure not shown]
#### **9.2.4. MEDICAL HISTORY**

[figure not shown]
Record all relevant ocular and relevant non-ocular medical history.

[figure not shown]

#### **9.3.7. ENDOTHELIAL CELL DENSITY ANALYSIS**

Endothelial cell density [REDACTED] will be measured using the same methods as in the previous studies (C-02-23, C-02-40, C-03-21, C-05-57). The Konan Noncon-Robo specular microscope will be used to photograph corneal endothelial cells. Three images at the center of the cornea [REDACTED] shall be obtained.

Images shall be stored on the computer hard drive at the clinical site. Electronic copies of the images will be sent to a central reading center for analysis. For consistency, the central reading center ([REDACTED]) used for the previous studies, will be used for this study; Alcon personnel will not be involved in image analysis. The process for analyzing images at [REDACTED] will remain unaltered from that done in previous studies. Briefly, images received at [REDACTED] [REDACTED] will be reviewed by an initial reader and assessed for image quality. If image quality is acceptable then images will be analyzed. If images are deemed unanalyzable, then images will not be analyzed, and the site and Sponsor will be notified. (If there is a trend of unanalyzable images for a specific site/delegated study

personnel, retraining will be provided.) The subject will be asked to return and repeat the image capture and new images will be analyzed and used in the dataset. Analyzed images will be audited by a quality control reviewer [REDACTED]

Data reported by the central reading center will include endothelial cell density, [REDACTED]

[REDACTED] The site will receive a copy of the analysis to enter results in eCRFs.

The critical ECD threshold needed to sustain corneal endothelial cell function varies among individuals. Thus, it is critical to have regular examinations of the cornea every 6 months.

[figure not shown]
Criteria that may warrant more frequent examinations include:

- <1500 cells/mm^2 (central [REDACTED])
- >10% ECL in one year
- >30% ECL from preoperative baseline

[REDACTED]

When the central ECD approaches approximately 1500 cells/mm^2, the investigator should consider the potential need to undergo IOL explantation to reduce the risk of corneal decompensation and subsequent surgical interventions (such as corneal transplantation or DSEK). [REDACTED]

[REDACTED]

#### **9.4. *Unscheduled Visits***

If a subject is examined more than once during any of the scheduled follow-up periods or if the subject is examined between scheduled follow-up periods, or if there is an unscheduled planned treatment delaying exit, an Unscheduled Visit Form must be completed.

If, during the visits for the 2nd eye implanted (Year 4A through 10A Forms), a clinically-relevant finding is noted for the 1st eye implanted, an unscheduled visit form must be completed to record the data for the 1st eye implanted; the same is true if a clinically-relevant finding is noted on the 2nd eye during the visits for the 1st eye. If the second eye examination is being conducted at the same time as a scheduled first eye examination (with both examinations occurring during the correct time frame) the findings from each eye should be recorded on the applicable visit form and not on an unscheduled visit form.

#### **9.5. *Missed Visit – “Subject Unavailable”***

If a subject unavoidably misses a scheduled exam, all reasonable efforts must be made to have the subject rescheduled within the same exam follow-up period. The investigator must show diligence in trying to schedule the subject for all of their postoperative exams. All attempts to contact the subject must be documented in the source documentation and the subject's medical records. If an exam cannot be rescheduled, the corresponding visit pages will be marked "missed visit, subject unavailable". Please do not classify the subject as "unavailable" until rescheduling has been attempted and the time frame for the postoperative exam has expired.

If a subject is unable to return for the final study visit (Year 10 or 10A), complete the Exit Form with the appropriate reason for discontinuation indicated.

### ***9.6. Discontinued Subjects***

Discontinued subjects will not be replaced. If a subject is discontinued from the study due to their death, the Exit Form and a Serious Adverse Event/Adverse Device Effect Form must be completed.

Subjects who require an IOL explant will not be discontinued and all reasonable efforts must be made to follow them up through their final study visit (Year 10/10A).

### ***9.7. Subject Lost to Follow-Up***

A subject is considered lost to follow-up if:

- a) a postoperative Study Visit is overdue, all efforts to contact the subject for an examination have failed, the subject's last visit window has closed, or
- b) the subject is unable to make future office visits, or
- c) the subject has moved and is no longer able to be examined.

If a subject moves before completing all of the required visits, reasonable efforts must be made for the subject to return to the implanting investigator or to the closest investigational site for follow-up. Reimbursement for reasonable travel costs may be available from the Sponsor and will be addressed on a case-by-case basis.

### ***9.8. Patient Pregnancy***

Subjects who become pregnant during the study will not be discontinued.

## **10. ANALYSIS PLAN**

### ***10.1. Subject Evaluability***

All subjects enrolled in the study will be considered evaluable for the safety analysis. The final evaluability (exclusion of post-explantation endothelial cell density data) will be determined prior to database lock.

### ***10.2. Analysis Data Sets***

#### **10.2.1. SAFETY**

All data collected in the study will be considered evaluable for the safety analysis with one exception. For subjects who have their ACRYSOF CACHET L-series Phakic Lens explanted and not replaced with another ACRYSOF CACHET L-series Phakic Lens, the post-explantation endothelial cell density data will be excluded from the statistical analyses. The post-explantation data will be used in subject narratives and graphs.

[figure not shown]
### ***10.3. Demographic and Baseline Characteristics***

[figure not shown]
Demographic and baseline information from the subjects' previous study will be summarized using frequency distributions for categorical parameters and descriptive statistics (number, median, minimum, maximum, mean and standard deviation) for continuous parameters.

### ***10.4. Safety Analysis***

The safety parameters include:

- Central Endothelial Cell Density
- Adverse Events

The primary objective is to estimate the annualized endothelial cell density loss rate (for up to 10 years following date of implantation) of subjects previously implanted with the ACRYSOF CACHET Phakic Lens (L-series) from clinical studies C-02-23, C-02-40, C-03-21 and C-05-57.

[figure not shown]
The secondary objective is to collect additional safety data that may identify risk factors for eyes with significant endothelial cell density loss.

#### **10.4.1. PRIMARY SAFETY**

##### **10.4.1.1. CENTRAL ENDOTHELIAL CELL DENSITY**

Descriptive statistics for central endothelial cell density, for each scheduled visit (including data from previous studies), will be provided. Descriptive statistics for central endothelial cell density chronic change (actual and percent) from baseline (6 month visit in previous study) to each scheduled visit will be provided. Descriptive statistics for central endothelial cell density change (actual and percent) between consecutive scheduled visits will be provided. All tables will be generated separately for first implanted eye, second implanted eye, and for both implanted eyes combined. Descriptive statistics include mean, median, standard deviation, sample size, minimum, maximum and confidence limits.

The mean rate of endothelial cell density decrease will be calculated via a paired analysis in order to calculate the mean of the differences between each reporting period.

[figure not shown]

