
No

Masking:

None

Observer-Masked

Patient-Masked

Double-Masked

Randomization:

Yes

No

Group Assignment Ratio:

Concurrent Control:

None

No Treatment

Placebo

Active

Other

Specify:  
Specify:

Estimated Total Sample Size: Required: N/A

Planned: Up to 1321 eyes

Statistical Rationale Provided:  Yes See Section 11

No

Variable(s): Primary Efficacy

- None

Secondary Efficacy

- None

Primary Safety

- Central endothelial cell density
- Adverse events

Adverse Events:

[figure not shown]
Both volunteered and elicited

Other:

Analyses: The primary objective is to estimate the annualized endothelial cell loss rate (for up to 10 years following date of implantation) of subjects previously implanted with the ACRYSOF CACHET Phakic Lens (L-series) from clinical studies C-02-23, C-02-40, C-03-21 and C-05-57.

[figure not shown]
Combining data from this study with the data from the subjects' previous studies, the rate of endothelial cell density loss between consecutive visits will be calculated via a paired analysis and descriptive statistics on those rates will be presented. [REDACTED]

[REDACTED] Also, the percentage endothelial cell density decrease for each eye from baseline (6 month visit in previous study) to each visit will be calculated via a paired analysis and descriptive statistics for the actual and annualized loss rates will be presented.

The secondary objective is to collect additional safety data that may identify risk factors for eyes with significant endothelial cell loss.

Descriptive statistics will be provided for central [REDACTED] endothelial cell densities, [REDACTED]

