## **5. OBJECTIVE(S)**

The primary objective is to estimate the annualized endothelial cell loss (ECL) rate (for up to 10 years following date of implantation) of subjects previously implanted with the ACRYSOF CACHET Phakic Lens (L-series) within clinical studies C-02-23, C-02-40, C-03-21 and C-05-57.

The secondary objective is to collect additional safety data that may identify risk factors for eyes with significant ECL.

[figure not shown]

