## 17. STUDY PLAN

**Table 17.-1:**  
**Study Plan**

Procedure / Assessment	Entrance Visit a	Nominal Time ± Visit Window Limits												
		Day 1429 – 1550	Day 1794 – 1915	Year 4/4A c	Year 5/5A d	Year 5.5/5.5A	Year 6/6A	Year 6.5/6.5A	Year 7/7A	Year 7.5/7.5A	Year 8/8A	Year 8.5/8.5A	Year 9/9A	Year 9.5/9.5A
Informed Consent	X				Day 1976 – 2097	Year 5.5/5.5A								
Inclusion/Exclusion	X				Day 2159 – 2280		Year 6/6A							
Enrollment Information e	X				Day 2341 – 2462	Year 6.5/6.5A								
Medical History	X				Day 2524 – 2645	Year 7/7A								
Central [REDACTED] [REDACTED] T Endothelial Cell Photography-3 images each		X	X	X	X	X	X	X	X	X	X	X	X	X

Adverse Events

(both volunteered  
and elicited)

X X X X X X X X X X X X

aThe subject's initial C-09-043 study examination may be Year 4 or later (i.e., Year 4, 5, 5.5, 6, etc.). Point of entry is determined by each subject's eye surgery date and the next available visit listed here to enable continued yearly examination. As in previous studies, subjects with the ACRYSOF CACHET Phakic Lens (L-Series) implanted in both eyes will have separate study visits, as needed, for each eye to capture the data within the window of the annual implant date anniversary.

bStudy Day is relative to the surgery date for each implanted eye.

[figure not shown]
cData from subject's 2nd implant surgery will be captured on Forms designated with an "A".

[figure not shown]
dA 4.5 Year visit is not included since all patients are past this time-point.

[figure not shown]
eThe Enrollment Information panel will collect basic information from the subject's previous study (e.g., protocol number, investigator number, subject number, and the first Form/Visit where data is captured in this study for each eye).

[figure not shown]

[figure not shown]

[figure not shown]

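### As readable, the consecutive-visit loss figures are not divided by time, and visit spacing halves after Year 5, so a constant loss could look like slowing loss

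*Protocol*

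**What the plan says.** Protocol section 5 sets the target: "The primary objective is to estimate the annualized endothelial cell loss (ECL) rate", for up to 10 years after implantation.

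Two places in the protocol describe a consecutive-visit analysis.

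- The protocol Summary, under the primary objective, describes it as follows: "the rate of endothelial cell density loss between consecutive visits will be calculated via a paired analysis and descriptive statistics on those rates". The text directly after that sentence is redacted.
- Section 10.4.1.1 says "Descriptive statistics for central endothelial cell density change (actual and percent) between consecutive scheduled visits will be provided". It then says that the mean rate of decrease "will be calculated via a paired analysis in order to calculate the mean of the differences between each reporting period". The term for the period is not defined in the readable text.

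Elsewhere the plan does annualise. For loss from the 6-month baseline, the Summary says "descriptive statistics for the actual and annualized loss rates will be presented". SAP 4.1.2.1 (from Month 6) and SAP 4.1.2.2 (from the preoperative baseline) also plan annualised percent change. The readable SAP contains no consecutive-visit analysis.

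On timing, protocol Table 17.-1 goes from Year 4 to Year 5 and then to half-yearly visits. A footnote explains the missing visit: "A 4.5 Year visit is not included since all patients are past this time-point". Protocol 9.1 also allows late exams into the Year 10 analysis, under listed conditions: "Subjects examined subsequent to Day 3740 and prior to study exit".

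**The concern.** A difference between two visits is a rate per year only if the visits are one year apart. Here they are a year apart before Year 5 and half a year apart afterwards. Undivided differences therefore mix cell loss with visit spacing. They cannot be compared across Year 5, or set beside the annualised figures from baseline, until they are corrected for interval length.

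The error would run in the reassuring direction. The consecutive-visit series is the readable analysis that shows most directly whether loss speeds up or slows down, because a from-baseline average smooths such changes. A step down at Year 5 that comes only from the schedule could be taken as evidence that loss is slowing, in a study whose purpose is long-term endothelial safety.

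**Working it through.** The plan states no loss rate, so there is no figure of its own to reproduce. The check is what a constant loss would look like on the planned schedule.

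**Inputs.** The windows come from protocol Table 17.-1, matched to visits by column order because the table is broken in the text. The annual loss is an assumption; 1% is used for display.

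| Visit | Window (days) | Midpoint |
|---|---|---|
| Year 4 | 1429–1550 | 1489.5 |
| Year 5 | 1794–1915 | 1854.5 |
| Year 5.5 | 1976–2097 | 2036.5 |
| Year 6 | 2159–2280 | 2219.5 |
| Year 6.5 | 2341–2462 | 2401.5 |
| Year 7 | 2524–2645 | 2584.5 |

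**Step 1: spacing.** The gap is the difference between consecutive midpoints: 365, 182, 183, 182 and 183 days. The ratio across Year 5 is 182/365 = 0.499.

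**Step 2: undivided loss per period.** Loss shown = annual rate × gap/365.25.

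- Year 4 to 5 at 1% per year: 1 × 365/365.25 = 0.999%.
- Year 5 to 5.5: 1 × 182/365.25 = 0.498%.
- Year 5.5 to 6: 1 × 183/365.25 = 0.501%.

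The halving does not depend on the assumed rate. At 0.5% per year the pair is 0.50% and 0.25%; at 2%, 2.00% and 1.00%; at 5%, 5.00% and 2.49% (2.52% if loss compounds).

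**Step 3: divide by time.** Rate = loss × 365.25/gap. Year 4 to 5 gives 0.999 × 365.25/365 = 1.00% per year. Year 5 to 5.5 gives 0.4983 × 365.25/182 = 1.00% per year. The step disappears.

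**Step 4: variation in actual visit days.** The shortest possible gap is the next window's start minus this window's end; the longest is the next end minus this start. Year 4 to 5 can be 244 to 486 days, and a half-yearly pair 61 to 304 days. At 1% per year, one eye could show 0.67% to 1.33% in the first case and 0.17% to 0.83% in the second. These are single-eye extremes. In a simulation of 1 million eyes (true loss 1% per year, visits uniform in their windows, mean density 2700 cells/mm², SD 12%, per-visit CV 2%, all assumed), the mean undivided loss was 25.9 and then 12.8 cells/mm², close to the 2:1 ratio of the midpoints. Divided by each eye's elapsed time, it was 25.9 and 25.7 cells/mm² per year, equal to the simulated true values.

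**Step 5: price of dividing.** In the same simulation the per-eye SD of the annual rate was about 76 cells/mm² per year for Year 4 to 5 and about 168 for Year 5 to 5.5. A rough check: measurement error alone gives a difference with SD √2 × 0.02 × 2700 = 76 cells/mm². Over half a year that becomes 76/0.5 = 153 per year, and unequal gaps raise it further.

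**The case against.** The strongest objection is that the formula may be in text that cannot be read. Redaction follows the consecutive-visit sentence in the Summary, section 10.4.1.1 ends in content not shown, and the SAP contents list a redacted entry between the chronic-loss section (page 10) and adverse events (page 15). This stands. The finding is that the readable text gives no divisor, not that the plan lacks one.

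Second, the wording may mean something else. Section 10.4.1.1 lists change and mean rate separately, so the rate may already be per unit time; and if the undefined period means one year, that mean would show no step. This also stands, but it leaves a definition to be stated. The separate tables of actual and percent change between scheduled visits would still cover unequal intervals.

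Third, a reader might infer that the primary objective has no annualised estimate. The documents do not support that: annualised loss is expressly planned from Month 6 and from the preoperative baseline.

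Fourth, tables by named visit pair let a careful reader see the unequal spacing, and no hypothesis test depends on them (protocol 10.7). That limits the harm but does not turn a per-period difference into an annual rate.

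Two further inferences go too far. The fivefold single-eye range in a half-yearly period largely averages out in the planned means. And although late Year 10 exams lengthen the last interval, nothing shows how many eyes would qualify or how late they would be, so no effect on the mean can be sized.

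**Conclusion.** The concern holds for the consecutive-visit figures as the readable protocol describes them. If those differences are left undivided, a constant loss shows about half as much per period after Year 5, at any plausible rate. The factor of one half rests on the readable windows to Year 7; beyond that, half-yearly spacing rests on the visit labels. The 1% per year is only for illustration.

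It would be too strong to say that the reported results will show this drop. That depends on a formula that may be stated in redacted text. If it already divides by time, what remains is to bring the readable wording into line. The annualised from-baseline estimates, and so the main answer to the primary objective, are not affected. This should be corrected, but it does not undermine the study.

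**What to change.** In protocol 10.4.1.1, the Summary and any matching SAP text:

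- Define the consecutive-visit rate for each eye as (earlier density − later density) / (elapsed days/365.25), in cells/mm² per year, with the percent version likewise per year. Use the actual days between the two exams, including exams after Day 3740 that are counted as Year 10.
- Summarise it with the statistics already planned: "Descriptive statistics include mean, median, standard deviation, sample size, minimum, maximum and confidence limits".
- Show the interval length on any per-period table that is kept, and define the reporting period.
- Where confidence limits are given for both eyes combined, use limits that allow for two eyes per subject, for example a bootstrap by subject. At the planned maximum of 1321 eyes in 778 subjects, 1321 − 778 = 543 subjects would contribute two eyes.

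Optionally, add a pooled percent rate: summed loss divided by the sum of earlier density × eye-years. It weights by follow-up time and is less affected by short gaps, but the bias it removes is negligible at a CV of 1% to 2%.

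The cost is some programming and a short method note; no data or visits are added. The drawback is noise: under the assumptions above, the per-eye SD rises from about 76 to about 168 cells/mm² per year in half-year intervals, so the minimum and maximum will look wide. A note under the table should say so.
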